12.7 Insurance

A certificate attesting Third Party coverage of CRO/Sponsor will be provided upon request.

12.8 Publication Policy

The Institution/Investigator and the Sponsor's obligations regarding intellectual property rights, confidentiality, and publications are described in detail in the Clinical Trial Agreement.

The aim is to submit the results of this study for publication in a public database (e.g., www.ClinicalTrials.gov) and to a medical journal for publication of the results. Everyone who is to be listed as an author of the results of this multicenter study shall have made a substantial, direct, intellectual contribution to the work. Authorship will be based on (1) substantial contributions to the conception or design of the work; or the acquisition, analysis, or interpretation of data for the work; and (2) drafting the work or revising it critically for important intellectual content; and (3) final approval of the version to be published; and (4) agreement to be accountable for all aspects of the work in ensuring that questions related to the accuracy or integrity of any part of the work are appropriately investigated and resolved.^a Conditions 1, 2, 3, and 4 must all be met in order to be

^a Defining the role of authors and contributors, compiled by the International Committee of Medical Journal Editors (ICMJE) (<http://www.icmje.org>).

Effective

Effective date: 2021-06-28 08:30

designated as author. Those who do not meet all four criteria will be acknowledged. Among the authors that fulfil the above mentioned criteria, one author will be appointed by the Sponsor to take primary responsibility for the overall work as primary author.

2.0

14 APPENDICES

[Appendix 1: Subject Satisfaction Questionnaire](#)

[Appendix 2: Physician Satisfaction Questionnaire](#)

[Appendix 3: Subject Self-Assessment of GL Severity Using The 4-point Categorical Scale](#)

CCI

Appendix 1 Subject Satisfaction Questionnaire

Subject #:

Visit #:

Date of questionnaire completion (DD/MM/YYYY):

Please tick the box corresponding to your preferred answer (only one box should be ticked by question unless otherwise specified).

Complete at Visit 1 ONLY

CCI

4. How satisfied have you been with the aesthetic outcome in the injected area after treatment?

[figure not shown]
- Very satisfied
- Satisfied
- Dissatisfied
- Very dissatisfied

5. How satisfied were you with the comfort of the injection?

- Very satisfied
- Satisfied
- Dissatisfied
- Very dissatisfied

Effective

Effective date: 2021-06-28 08:30

Effective date: 2021-06-28 08:30

CCI

Effective**Complete at Visit 6 ONLY****17. What is your overall satisfaction after three treatment cycles with *Dysport*?**

- Very satisfied
- Satisfied
- Dissatisfied
- Very dissatisfied

Appendix 2 Physician Satisfaction Questionnaire

[figure not shown]
Subject#:

Visit #:

Date of questionnaire completion (DD/MM/YYYY):

Please tick the box corresponding to your preferred answer (only one box should be ticked by question unless otherwise specified).

CC1

Effective date: 2021-06-28 08:30

**Complete at Visits 6 ONLY****7. What is your overall satisfaction after three treatment cycles with *Dysport*?**

- Very satisfied
- Satisfied
- Dissatisfied
- Very dissatisfied

Effective

Appendix 3 Subject Self-Assessment of GL Severity using the 4-point Categorical Scale

Subject#:

Visit #:

Date of completion (DD/MM/YYYY):

Subject Instructions: Using a mirror, evaluate your ‘glabellar lines’ (the lines between your eyebrows) while you are frowning. To produce a ‘max frown’ you are to raise your eyebrows, then bring them together as strongly as you can. You may repeat this until you are comfortable with frowning. Evaluate your lines at max frown according to these four categories shown below.

These assessments will be repeated at each visit in the study center and we will ask that you make the max frown in exactly the same way on each occasion. Please place a mark (X) in the box that best describes how you think the lines between your eyebrows look when frowning today.

At max frown:

No wrinkles (smooth skin)	Mild wrinkles (fairly smooth skin)	Moderate wrinkles (glabellar lines)	Severe wrinkles (severe glabellar lines)

Please be advised that you will be using the same scale to rate the appearance of your glabellar lines at every visit.

Note: The subject should perform their self-assessment independently of the physician’s assessment.

Note: With guidance from the physician, subjects may also reference the **CCI**
CCI when completing their self-assessment.

Effective

Effective date: 2021-06-28 08:30

2.0

Effective

Effective date: 2021-06-28 08:30

CCI

2.0

Effective date: 2021-06-28 08:30

Investigator's Validated 4-point Photographic Scale

[figure not shown]
At Rest

Characterized by muscle activity at the time of evaluation having limited impact on their presence or absence

GRADE 2: MODERATE / 中度

GRADE 3: SEVERE / 重度

PPD

Dermal crease – A deep linear depression in the skin surface that is deeper and/or wider than a fine wrinkle distinguishable from a dermal groove by the absence of muscle contractions at rest.

Dermal groove – A deep linear depression in the skin surface distinguishable from a dermal crease by the presence of persistent muscle contraction or spasm visible when the patient is "at rest".

Effective

2.0

Effective date: 2021-06-28 08:30

Investigator's Validated 4-point Photographic Scale

At Max Frown

Glabellar lines produced by maximal voluntary muscular activity contributing to the presence of the lines

GRADE 0: NONE / 无

GRADE 1: MILD / 轻度

PPD

Relaxed skin tension line; no wrinkles

Glabellar depression(s) – A mild depression(s) in the glabellar area (inter-brow space) surrounded by mild bulging of the glabellar muscles.

Effective date: 2021-06-28 08:30

Investigator's Validated 4-point Photographic Scale

At Max Frown

Glabellar lines produced by maximal voluntary muscular activity contributing to the presence of the lines

GRADE 2: MODERATE / 中度

GRADE 3: SEVERE / 重度

PPD

Glabellar groove – Moderate depression(s) of the inter-brow space surrounded by moderate to significant muscle contraction and bulging.

Glabellar furrow – Deep groove(s) in the glabellar area (inter-brow space) surrounded by profound muscle contraction and bulging.

Effective date: 2021-06-28 08:30

8. REFERENCE.....	17
9. TFL SHELL	17

ABBREVIATION

Abbreviation	Specification
AE	Adverse Event
AE	Adverse Event
ATC	Anatomical Therapeutic Chemical
BoNT	Botulinum toxin
BoNT-A	Botulinum toxin serotype A
CI	Confidence Interval
CRF	Case Report Form
CSR	Clinical Study Report
GCP	Good Clinical Practice
GL	Glabellar lines
FAS	Full Analysis Set
ICH	International Council for Harmonization
IP	Investigational Product
MedDRA	Medical Dictionary For Regulatory Activities
NA	Not Applicable
NMPA	National Medical Products Administration
PPS	Per Protocol Set
PT	Preferred Term
Q1	25% quartile
Q3	75% quartile
SAE	Serious Adverse Event
SAP	Statistical Analysis Plan
SAR	Statistical Analysis Report
SAS	Statistical Application Software
SD	Standard Deviation
SOC	System Organ Class
TEAE	Treatment Emergent Adverse Events
SS	Safety Set
SS Event	Special Situation Event
UAE	Unexpected Adverse Drug Reaction
WHO DD	World Health Organization Drug Dictionary

1. INTRODUCTION

This Statistical Analysis Plan (SAP) describes the statistical methods that will be used in summarizing and analyzing the efficacy and safety data that will be collected in this study 05PF2009 and aims to support the clinical study report (CSR). This statistical analysis plan will be finalized prior to database lock.

This document is developed based on the protocol version 2.0 (28 Jun 2021) and electronic Case Report Form (eCRF) version 1.1 (01 Jan 2023) and compliances with the recommendations of the International Conference on Harmonization (ICH) E9 guidelines “Statistical Principles for Clinical Trials”^[1] and the ICH E3 guidelines “Structure and Content of Clinical Study Reports”^[2].

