10 STATISTICAL METHODS PLANNED

10.1 Statistical and Analytical Plans

A Statistical Analysis Plan (SAP) will be developed as a separate document. The SAP will contain a more detailed and technical description of specific data conventions, calculations and of statistical procedures for executing the analyses that are specified in the sections of the clinical study protocol below. The SAP will be finalized prior to FSFV.

Any change made to the finalized SAP will be documented in the Clinical Study Report (CSR).

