10.1.2 Populations Analyzed and Evaluability

The primary analysis will be performed on the enrolled population. Analysis on the per-protocol (PP) population maybe performed, if needed.

The rules for the allocation of subjects to each of the analysis populations will be defined and documented during a data review meeting held prior to database lock.

During the data review meeting, based on minor or major protocol deviations recorded, subjects may be excluded from the PP population.

Subjects may be excluded from the analyses if one or more of the following deviations occur.

- Subject did not complete the study
- Violation of inclusion/exclusion criteria

10.1.2.1 *Enrolled Population*

The enrolled population includes all subjects who are enrolled in the study treated at least once with *Dysport*.

10.1.2.2 *Per-protocol (PP) Population*

The Per Protocol (PP) population is a subset of the enrolled subjects who have no major protocol deviations, as outlined above.

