10.3 Analysis

Since this is an open non-interventional study, available data may be analyzed prior to study completion.

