7.6. Interim Analyses

Two interim analyses will be performed before the final analysis. The first interim analysis will be performed after Visit 2. The second interim analysis will be performed after Visit 4. Only applicable tables and listings will be generated for interim analyses.

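### SAP 1 lets the plan be finalised as late as database lock, where the protocol says before the first subject's first visit; SAP 7.7 declares neither this nor the move of the main efficacy set to the PPS

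*SAP*

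**What the plan says.** **When the plan is fixed.** Protocol 10.1 says "The SAP will be finalized prior to FSFV", and adds that later changes to the finalised SAP are to be documented in the clinical study report (CSR). SAP 1 says "This statistical analysis plan will be finalized prior to database lock".

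**Looks at the data.** Protocol 10.3 allows early analysis: "Since this is an open non-interventional study, available data may be analyzed prior to study completion". SAP 7.6 makes this concrete: "The first interim analysis will be performed after Visit 2. The second interim analysis will be performed after Visit 4". It adds: "Only applicable tables and listings will be generated for interim analyses". There is no blinding (SAP 3.5).

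**Main efficacy set.** Protocol 10.1.2 says "The primary analysis will be performed on the enrolled population" and leaves a per-protocol analysis optional. SAP 7.1.1 reverses the order, with the PPS as the main basis for efficacy and the FAS as reference. SAP 7.4.1 reports the primary endpoint on both.

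**Who decides membership.** Protocol 10.1.2 says "The rules for the allocation of subjects to each of the analysis populations will be defined and documented during a data review meeting", held before database lock. SAP 6.2 likewise leaves PPS exclusions to that meeting, and Protocol 10.1.5 leaves subgroups to it.

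**Declared changes.** SAP 7.7 lists three: the two interim analyses, the deleted adverse drug reaction definition, and the replacement of unexpected adverse drug reactions by unexpected adverse events.

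**The concern.** A plan fixed before the first visit cannot be shaped by the results. A plan that need only be fixed before lock can be, and here two open analyses come first. The subject questionnaire is completed at every visit, so satisfaction data exist at both looks whether or not any Visit 6 answer does.

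The protocol's safeguard is the CSR record of changes to the finalised SAP, and it starts only at finalisation. Until then the wording can be altered without that record. The choice most exposed is which analysis set supplies the result presented as main. That choice already differs from the protocol, and SAP 7.7 does not say so.

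**Working it through.** No sample size, power or alpha calculation can be reproduced: the target of about 250 is not calculated (SAP 3.6) and no hypothesis is stated (SAP 5). The check is a comparison of texts, followed by two short derivations that limit the consequence.

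**1. Comparison**

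| Item | Protocol | SAP | Declared in SAP 7.7? |
|---|---|---|---|
| SAP final by | first subject's first visit (10.1) | database lock (1) | No |
| Main efficacy set | enrolled population (10.1.2) | PPS (7.1.1) | No |
| Early analyses | allowed (10.3) | two, after Visits 2 and 4 (7.6) | Yes |
| PPS membership | data review meeting (10.1.2) | data review meeting (6.2) | No change to declare |

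The first two rows are undeclared departures. The last is not a departure.

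**2. Order of milestones**

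Inputs: 1 month = 4 weeks (Protocol Table 2, SAP 3.3); recruitment about six months, so 24 weeks (Protocol 4); injections 12 to 24 weeks apart; follow-up 2 to 4 weeks after injection. Week 0 is the first subject's first injection.

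- Last subject's Visit 2: 24 + 2 to 24 + 4 = weeks 26 to 28.
- Last subject's Visit 4: 24 + 12 + 2 to 24 + 24 + 4 = weeks 38 to 52.
- Last subject's Visit 7: 24 + 36 to 24 + 72 = weeks 60 to 96.

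SAP 7.6 places both looks before the final analysis. If each waits for the last subject, the lock follows the second look by weeks to months, and sign-off in that gap would satisfy SAP 1.

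**3. Could Visit 6 answers be on file at a look?**

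Assume that each look is cut when the last subject reaches the named visit, entry is even over 24 weeks, no one drops out, follow-up is at 3 weeks, and all injection intervals equal I. The second look is at week 24 + I + 3. A subject entering at week t reaches Visit 6 at t + 2I + 3. The answer is on file if t ≤ 24 − I, a share of (24 − I)/24.

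- I = 12: 12/24 = 50%.
- I = 18: 6/24 = 25%.
- I = 24: 0%.

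These are illustrations, not bounds. If the last subject's first interval is 24 weeks and all other intervals are 12, the look is at week 24 + 24 + 3 = 51. Everyone else reaches Visit 6 by 24 + 27 = 51, giving 249/250 = 99.6%. At the first look (week 24 + 3 = 27) the earliest Visit 6 is at 12 + 12 + 3 = week 27, so essentially none are on file unless the visit windows are pushed to their limits. All these shares count answers on file, not answers shown or used. SAP 7.6 does not say whether Visit 6 answers already collected would appear.

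**4. How PPS and FAS can differ on the primary endpoint**

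Percentages use non-missing data (SAP 7.1.2) and nothing is imputed (SAP 7.2). The FAS denominator is therefore the n Visit 6 responders. Taking an evaluable primary endpoint to mean an answer at Visit 6, that PPS criterion removes no one from the n. If k responders are excluded for deviations or compliance, then for any response category

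p(FAS) − p(PPS) = (k/n) × [p(excluded) − p(PPS)].

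Neither k nor the excluded subjects' answers can be known from the documents, so no shift can be computed. Non-completion is one possible ground for exclusion in Protocol 10.1.2, so a Visit 6 responder who missed Visit 7 could be among the k.

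**The case against.** **No late sign-off is shown.** This stands. Database lock is an outer limit, which sign-off before the first interim would also meet. A reader might infer late sign-off because the SAP builds on an eCRF version dated 01 Jan 2023, 552 days after the protocol version of 28 Jun 2021. That makes finalisation before the first visit look unlikely but does not prove it, and it says nothing about sign-off relative to the interims. The first-visit, interim and sign-off dates are not in the available text.

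**Choice of PPS members and subgroups does not come from SAP 1.** This also stands. It is tempting to argue that late sign-off lets PPS membership and subgroups be picked after answers are seen. The protocol already places both at the pre-lock data review meeting, so a SAP signed before the first visit with the same text would leave that exposure unchanged. The protocol's sentence "Subjects may be excluded from the analyses if one or more of the following deviations occur" names grounds such as non-completion. It does not expressly limit itself to the per-protocol set, but the definition of that set refers back to it.

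**The interims add little.** This stands in part. Protocol 10.3 allows early analysis, and the natural reading of SAP 7.6 is that Visit 6 tables are not applicable at either look. The SAP does not say so, however, and earlier satisfaction answers would be seen in any case.

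**Database lock might mean an interim lock.** The SAP defines none, so this reading has no support in the text.

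**A descriptive study has no error rate to protect.** This is correct, and it limits the weight of the point. It does not answer the two undeclared departures in the comparison table.

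**Conclusion.** The point holds as a conflict between two stated milestones, together with an incomplete declaration of changes. The added exposure is narrow: SAP text, above all the choice of main set, may be altered after satisfaction data are seen and without the CSR record that would follow finalisation.

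Severity is minor to moderate. The FAS matches the enrolled population in substance and is reported beside the PPS with exact intervals. PPS choices therefore cannot alter the FAS result, only the result presented as main. A reader might take the Visit 6 shares as a measure of bias. They are not: they depend on an assumed cut-off rule and on injection intervals that the documents leave open. Nor do the documents support a statement that the plan was in fact signed after an interim look.

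**What to change.** 1. **SAP 1:** finalise the SAP before the data cut-off of the first interim analysis. Since that is still later than Protocol 10.1 requires, record the departure in SAP 7.7. If the cut-off has passed, state the actual first-visit, interim and sign-off dates and disclose the departure in SAP 7.7 and the CSR.
2. **SAP 7.1.1:** restore the enrolled population (FAS) as the main efficacy set with the PPS as supportive, or declare and justify the change in SAP 7.7.
3. **Data review meeting:** decide PPS exclusions from listings that show whether the primary question was answered but not the satisfaction or severity answers. The protocol does not require this; it is a cheap precaution against an exposure that the protocol itself leaves open.
4. **SAP 7.6:** limit the outputs of the two interim analyses to data up to Visit 2 and Visit 4 respectively.

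The cost is an earlier sign-off and slightly less flexibility at the data review meeting. No endpoint, sample size or study procedure changes.

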2. STUDY OBJECTIVE

To collect subject and physician satisfaction, and treatment experience with Dysport in real clinical practice in subjects of Chinese origin.

3. STUDY DESIGN

[figure not shown]
This is a prospective, longitudinal, non-interventional, multi-center study.

3.1. Investigational Product (IP)

Commercially available Dysport, a BoNT-A product, strength: 300U per vial, produced and supplied by Q-Med AB, part of the Galderma Group.

3.2. Study Flow Chart

Study Flow Chart is shown below.

3.3. Schedule of Assessments

Schedule of Assessments of the study is shown below.

Visit Number	Injection Cycle 1		Injection Cycle 2		Injection Cycle 3		Visit 7
	Visit 1 ¹	Visit 2	Visit 3	Visit 4	Visit 5	Visit 6	
Visit Name	Screening Baseline/ Injection 1 ¹	Follow up 1	Injection 2	Follow up 2	Injection 3	Follow up 3	Follow up 4
Visit Window	≤ 30 days of Baseline/ Injection 1	3 weeks (± 7 days) from Injection 1	3-6 months from Injection 1	3 weeks (± 7 days) from Injection 2	3-6 months from Injection 2	3 weeks (± 7 days) from Injection 3	3-6 months from Injection 3
Informed Consent	X						
Demographic Data	X						
Medical History	X						
Safety Review	X	X	X	X	X	X	X
Injection Practice Details	X		X		X		
Physician GL Severity Assessment	X ²	X	X ²	X	X ²	X	X
Physician Satisfaction Questionnaire	X ²	X	X ²	X	X ²	X	X
Subject assessments							
Subject GL Severity Assessment	X ²	X	X ²	X	X ²	X	X
Subject Satisfaction Questionnaire	X ²	X	X ²	X	X ²	X	X

Definitions:

- 1 month = 4 weeks

1. Screening and Baseline/Visit 1 (i.e., Injection 1) may be performed on the same day. If performed as separate visits, informed consent, demographic data, and medical history should be complete at Screening, and all other remaining visit procedures and confirmation of subject medical history should be performed at Baseline /Visit 1 (i.e., Injection 1).
2. Prior to injection.

3.4. Randomization Design and Execution

Not applicable. This is a non-interventional study.

3.5. Blinding Design and Execution

Not applicable. This is a non-interventional study.

3.6. Sample Size Consideration

The sample size of approximately 250 subjects is not based on a statistical calculation. The selected number of subjects is regarded as sufficient for an evaluation of the studied endpoints by using descriptive statistics.

4. ENDPOINTS

4.1. Efficacy Endpoints

4.1.1. Primary Efficacy Endpoints

The primary efficacy endpoint is subject satisfaction after three injection cycles with Dysport with GL. At Visit 6 subjects will be asked “What is your overall satisfaction after three treatments cycles with Dysport?” Response options are: very satisfied, satisfied, dissatisfied, and very dissatisfied. The primary endpoint will evaluate the proportion of subjects in each response category.

4.1.2. Secondary Efficacy Variables

- ① Physician satisfaction after three injection cycles with Dysport in the GL. The proportion of subjects in each response category for the physician's overall satisfaction with Dysport at Visit 6.
- ② a. Proportions of subjects in each response category per question answered on the Subject Satisfaction Questionnaire complete at all visits.

CCI

4.2. Safety Endpoints

4.2.1. Adverse Event (AE)

Any untoward medical occurrence in a patient or clinical investigation subject administered a pharmaceutical product and which does not necessarily have a causal relationship with this treatment.

An AE can therefore be any unfavorable and unintended sign (including an abnormal laboratory finding), symptom, or disease temporally associated with the use of a medicinal product, whether or not related to the medicinal product.

Thus, any new sign, symptom or disease, or any clinically significant worsening of an existing sign, symptom or disease (including new episodes of a chronic disease) compared to the condition at the first visit, should be considered as an AE.

4.2.2. Unexpected Adverse Event (UAE)

An unexpected AE is defined as an adverse event, the nature or severity of which is not consistent with the applicable study product information (e.g., medicinal package insert/summary of product characteristics for an approved study product).

4.2.3. Serious Adverse Event (SAE)

A SAE is any untoward medical occurrence that at any dose:

- (1) Results in death
- (2) Is life-threatening
- (3) Requires inpatient hospitalization or prolongation of existing hospitalization
- (4) Results in persistent or significant disability/incapacity
- (5) Is a congenital anomaly/birth defect

4.2.4. Special Situation (SS) Events

SS Event is an incidence of overdose, off-label use, medication error, occupational exposure, abuse, misuse, or lack of therapeutic efficacy while using the medicinal product, or any instance of drug exposure during pregnancy or breast-feeding.

